### **C. Adults' dosage regimen**

Oral administration

1) Initial dose and dosing schedule: sirolimus 2mg, once a day. Maintain drug trough concentration of 5-10ng / mL in blood. If adverse events are too severe to tolerate, daily dosage can be reduced by 0.5mg every week. The minimum dosage is 1 mg/day. If patient still cannot tolerate minimum dosage, withdraw from the study. If patient could tolerate the possible adverse events, continue to take the original dose for 3 months, and evaluate improvement of disease condition.

2) Subsequent dose and dosing schedule: After taking sirolimus 2 mg once a day for 3 months, those with improved condition continue to take the original dose. If improvement of disease condition is not obvious, change dosage to 2.5mg-3mg once a day. If this dosage cannot be tolerated, patients may withdraw from the study. If it can be tolerated, continue to take for another 3 months and reassess the improvement of condition.

3) Blood drug concentration test: Blood samples are taken at 1st, 3rd and 6th months of dosage schedule.

4) Iron supplementation: For subjects with hemoglobin  $\leq$  10.9 g / dl, iron supplementation should be provided according to the standard dosing regimen, but iron supplementation is

not considered as study treatment and will be recorded as concomitant medication.

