## **VI. Follow-up plan and content**

### **A. Evaluation before the trial**

Each subject should complete the following items in four weeks before the treatment:

- 1) Complete medical history
- 2) Detailed personal profile
- 3) VAS pain score
- 4) Quality of Life (Qol) Rating Scale
- 5) Frequency of blood transfusion therapy
- 6) A physical examination
- 7) Blood and urine routine examination
- 8) Liver and kidney function, blood lipid test
- 9) Coagulation I+D dimer examination
- 10) abdominal and pelvic cavity contrast-enhanced CT + small intestine reconstruction CT examination (for patients with gastrointestinal system affected)
- 11) Digestive system endoscopy (for patients with gastrointestinal system affected)
- 12) Ultrasound, MRI examination of the lesion
- 13) (Female of childbearing age) blood/urine pregnancy test

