### **B. Evaluation during sirolimus treatment**

Adverse reactions are evaluated weekly during the first month of drug treatment. The efficacy and safety are then evaluated at the 3rd and 6th months, and the content of the examination is the same as the pre-trial evaluation.

- 1) Efficacy assessment:
  - a. Clinical symptom assessment (including VAS pain score, gastrointestinal bleeding, quality of life (Qol) evaluation, frequency of blood transfusion treatment and other related symptoms);
  - b. Changes in hemoglobin;
  - c. Coagulation I+D-dimer examination;
  - d. Nutritional status (including albumin, etc.);
  - e. Ultrasound, MRI examination of the lesion, abdominal and pelvic cavity contrast-enhanced CT + small intestine reconstruction CT examination, digestive system endoscopy to measure the size, quantity and total load of VM lesions;
- 2) Safety assessment: Safety parameters (such as asking adverse events, measuring laboratory values, vital signs, gastrointestinal bleeding, etc.) will be closely monitored on a regular basis throughout the study.
- 3) Treatment compliance: In order to monitor compliance, subjects are required to complete an electronic diary during the entire study period. Dates of drug intake will be tracked by this diary. At every visit, the investigator and the subject will review the electronic diary data together.

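### The month-3 adult dose increase is triggered by lack of response alone, without using the trough drawn that month, and the next dated trough and safety visit come three months later

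*Combined protocol and SAP*

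**What the plan says.** Section V.C (Adults' dosage regimen) starts adults on 2 mg once daily and gives a standing exposure instruction: "Maintain drug trough concentration of 5-10ng / mL in blood". Item 1 allows weekly reductions of 0.5 mg, down to 1 mg/day, but only for adverse events too severe to tolerate. It states no action for a trough above 10 ng/mL.

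Item 2 governs month 3. Adults who have improved stay on 2 mg. For the others: "If improvement of disease condition is not obvious, change dosage to 2.5mg-3mg once a day". Those who cannot tolerate the higher dose may withdraw. Those who can are to "continue to take for another 3 months and reassess the improvement of condition".

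Item 3 dates the drug levels: "Blood samples are taken at 1st, 3rd and 6th months of dosage schedule".

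Section VI.B dates the safety checks: "Adverse reactions are evaluated weekly during the first month of drug treatment", and "The efficacy and safety are then evaluated at the 3rd and 6th months", with the same content as the baseline work-up. That content includes blood and urine routine and "Liver and kidney function, blood lipid test". Item 2 of VI.B adds that safety parameters, with adverse events, laboratory values and vital signs among the examples, "will be closely monitored on a regular basis throughout the study". It gives no interval, and drug level is not among the examples.

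**The concern.** The plan states an exposure ceiling and draws a trough at the visit where the dose decision is made, but the decision rule does not refer to that trough. An adult already in the upper part of the target range who has not improved is to be raised in the same way as one in the lower part.

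After the increase, no trough is dated for three months. A new dose of 2 mg is followed by weekly adverse-reaction checks for a month and a trough at month 1. The step to the highest adult dose, given to patients who have not clearly benefited, has no dated equivalent.

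Two things are at stake. For the patient, exposure above the plan's own ceiling could last until month 6 with no dated measurement to show it. For the trial, safety is the first objective in section II. A laboratory change that first comes to light at month 6 could not be matched to the trough at its onset, which weakens what can be said about safety at 2.5-3 mg.

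**Working it through.** **Schedule around each new dose.** All dates are from V.C items 1-3 and VI.B.

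| | Start of 2 mg (month 0) | Increase to 2.5-3 mg (month 3) |
|---|---|---|
| What decides the dose | Fixed starting dose | Response only |
| Dated adverse-reaction checks in the following month | Weekly (four) | None |
| First dated trough afterwards | Month 1 | Month 6 |
| Undated safety monitoring (VI.B item 2) | Applies | Applies |

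The gap from the increase to the next dated trough is 6 - 3 = 3 months. That is 3/6 = 50% of the six-month minimum treatment in section III.

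**Size of the increase.** 2.5/2 = 1.25 and 3/2 = 1.50, so 25% and 50%.

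**Month-3 trough at which the ceiling would be passed.** The documents give no dose-exposure relation, so assume trough ∝ dose^k. The month-3 trough that leads to exactly 10 ng/mL is 10 / ratio^k.

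| k (assumed) | 2.5 mg | 3 mg |
|---|---|---|
| 0.8 | 8.4 | 7.2 |
| 1.0 (proportional) | 10/1.25 = 8.0 | 10/1.50 = 6.7 |
| 1.2 | 7.7 | 6.1 |

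With k = 1, a trough in the 5-10 range becomes 6.25-12.5 on 2.5 mg or 7.5-15 on 3 mg. At the low end, adults below 5/1.25 = 4.0 (2.5 mg) or 5/1.50 = 3.3 (3 mg) would still be under 5 after the increase. The month-3 trough is therefore informative in both directions.

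**How many adults could be affected.** The documents give no trough distribution, so this is illustration only. Take lognormal month-3 troughs with a coefficient of variation of 30-40% and k = 1. The share of in-target adults who would pass 10 is P(limit < trough ≤ 10) / P(5 ≤ trough ≤ 10). The share of all adults who would move from in target to above 10 is the numerator alone. Both suppose that everyone is raised.

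| Median trough (assumed) | In-target adults: 2.5 mg / 3 mg | All adults: 2.5 mg / 3 mg |
|---|---|---|
| 4 ng/mL | 4-10% / 18-31% | 1-3% / 4-8% |
| 5 ng/mL | 9-16% / 32-41% | 5-8% / 15-19% |

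At a median of 4, 72-78% of adults are below 5 before any increase, so few are near the ceiling. At a median of 7, the in-target shares are 28-30% on 2.5 mg and 59-60% on 3 mg. The result depends almost wholly on where troughs sit, which the plan does not tell us.

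**The case against.** The strongest reply is that the target is a standing instruction. A trough is drawn at month 3, and 2.5-3 mg is a range, so a careful investigator could already decline to raise someone near 10 ng/mL. That is fair, and it makes the first half of the fix a clarification. It does not answer the second half: whatever was decided at month 3, no dated trough shows whether the new dose kept the patient in range until month 6.

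A reader might infer that laboratory values go unmeasured between months 3 and 6. The documents do not support this. VI.B item 2 names laboratory values among the parameters monitored regularly throughout. The fair criticism is that no interval is given. For the same reason, a calculated delay to detection that counts only the dated visits would overstate the wait. Nor is it right that the trough is never checked again, since a month-6 sample is planned.

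Symptomatic reactions are also better covered than the visit dates suggest. Section VII (Record and report) requires time and duration for each adverse event, serious events are reported to the principal investigator within 24 hours, and intolerance allows withdrawal. These provisions respond to symptoms or events; none of them measures drug level.

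The sampling months might have been meant to restart at the new dose, which would put a trough at month 4. Treatment is for at least six months, so the second period is not capped at three and this reading cannot be excluded. But the text does not say it, and sites could not be expected to apply it uniformly.

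Finally, a step of 25-50% in someone who has already taken 2 mg for three months is not the same as first exposure. That argues against copying the full weekly schedule, but not against one check.

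**Conclusion.** The point holds as a narrow gap in dosing and trough timing. As written, the rule can take an in-target adult past the plan's own 10 ng/mL ceiling, with no dated trough or dated safety visit for three months and no stated action on a high trough. The schedule part needs no assumption. The limits of about 8.0 and 6.7 ng/mL rest on assumed dose proportionality and shift to 7.7-8.4 and 6.1-7.2 over the exponents tried.

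A reader might go further and quote a percentage of adults who will exceed the ceiling. The documents support no such figure: the shares above depend on invented trough distributions, and the problem is small if troughs run low. The documents also do not say that harm begins at 10 ng/mL; it is simply the limit that the plan sets itself.

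The change should be made because it is cheap and serves the first objective. Confidence is medium, since the practical size depends on troughs that are not reported.

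**What to change.** In V.C item 2, state that the month-3 trough is reviewed before any increase, and that the dose is not raised to a level expected to take the trough above 10 ng/mL. Give about 8.0 ng/mL (for 2.5 mg) and 6.7 ng/mL (for 3 mg) as guides, not hard limits. If trough rises faster than dose (k = 1.2), 8.0 × 1.25^1.2 = 10.5 and 6.7 × 1.50^1.2 = 10.9, so patients at the guide values would still pass 10. The later trough is what catches them.

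In V.C item 3, add a trough about one month after any dose increase, together with blood count, liver and kidney function, lipids and an adverse-reaction check. State that the dose is reduced by 0.5 mg if that trough is above 10 ng/mL.

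The cost is one extra blood draw and contact per increased adult. If 5 to 15 of 20 patients were increased (assumed; 20 is the minimum enrolment), that is 5 to 15 of each. The month-3 result must be back before the new dose starts, which means a short wait. Some adults who have not improved but have high troughs would stay on 2 mg and forgo a trial of the higher dose, one that would be expected to exceed the plan's own ceiling.

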## **VI. Follow-up plan and content**

### **A. Evaluation before the trial**

Each subject should complete the following items in four weeks before the treatment:

- 1) Complete medical history
- 2) Detailed personal profile
- 3) VAS pain score
- 4) Quality of Life (Qol) Rating Scale
- 5) Frequency of blood transfusion therapy
- 6) A physical examination
- 7) Blood and urine routine examination
- 8) Liver and kidney function, blood lipid test
- 9) Coagulation I+D dimer examination
- 10) abdominal and pelvic cavity contrast-enhanced CT + small intestine reconstruction CT examination (for patients with gastrointestinal system affected)
- 11) Digestive system endoscopy (for patients with gastrointestinal system affected)
- 12) Ultrasound, MRI examination of the lesion
- 13) (Female of childbearing age) blood/urine pregnancy test

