#### **B. Exclusion criteria**

- (1) Patients need emergency surgery due to intestinal obstruction, intussusception, or gastrointestinal bleeding;
- (2) History of surgery within 1 month;
- (3) Allergic to rapamycin;
- (4) Any disease or condition that may affect the study implementation or result interpretation, including:
  - a) known hemoglobinopathy
  - b) concomitant gastrointestinal infections
  - c) severe heart, liver, kidney and other serious concomitant diseases that may endanger lives
- (5) Pregnant or lactating women;
- (6) Alcohol or drugs (eg, laxatives) abusers;
- (7) Participate in another clinical trial that may affect his or her study within one month;
- (8) The investigator believes to be not suitable for other reasons.

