## **V. Therapeutic schedule**

### **A. Enrollment**

Before starting the study, the investigator clearly and colloquially explains the study and its potential risks and benefits to the patient or his/her authorizer. Patient or his/her authorized and the investigator sign and date the informed consent form. Only after signing the informed consent form can patient or his/her authorizer enter the screening section. Patients who sign a written informed consent need to be assessed to determine if the patient meets the study criteria:

- 1) Demographic data and medical history of the patient;
- 2) vital signs;

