### **B. Children's dosage regimen**

Oral administration

The initial dose of oral rapamycin intake is 1 mg/m^2 of body surface area. Drug trough concentration in patient's blood is maintained at 5-10 ng/ml.

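### In the text supplied, the only pregnancy test before dosing may be up to 28 days old at the first dose of sirolimus, and neither dosing section requires a current result

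*Combined protocol and SAP*

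**What the plan says.** Section IV.B, criterion (5), excludes "Pregnant or lactating women". Section IV.A, item (2), sets no limit on age or sex, so women who could become pregnant can enrol.

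The pregnancy test stands in section VI.A, item 13: "Female of childbearing age) blood/urine pregnancy test". It has no timing rule of its own. It falls under the heading sentence for the whole list: "Each subject should complete the following items in four weeks before the treatment".

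Three other places could have set a closer check:

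- **Section V.A (enrolment)** says "Patients who sign a written informed consent need to be assessed to determine if the patient meets the study criteria". The list that follows shows demographic data with medical history, then vital signs, and stops on a semicolon.
- **Section V.B (children)** begins with "The initial dose of oral rapamycin intake is" followed by a dose per body surface area. It mentions no pregnancy test.
- **Section V.C (adults)** begins with "Initial dose and dosing schedule: sirolimus 2mg, once a day". It mentions no pregnancy test either.

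After treatment starts, section VI.B says "Adverse reactions are evaluated weekly during the first month of drug treatment", and section V.C, item 3, says of drug levels "Blood samples are taken at 1st, 3rd and 6th months of dosage schedule". Section VI.B gives the month-3 and month-6 evaluations the same content as the pre-trial evaluation, so the pregnancy test recurs there. Section VI.C does the same for the evaluations at the end of treatment and six and twelve months later.

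**The concern.** An exclusion criterion protects a participant only if it is checked close enough to the first dose for the answer still to hold. Medical history, imaging and endoscopy can reasonably share a four-week window. Pregnancy status is different, because it can change from negative to positive within those four weeks, and the test is quick to repeat.

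What is at stake is safety. A woman who tests negative early in the window and conceives before the first dose would start a drug that the protocol says she should not receive, with no listed step missed. No outside claim about sirolimus is needed: the protocol itself makes pregnancy a bar to entry and counts congenital malformations among serious adverse events (section VII.A). In the text supplied, sections IV.A and IV.B set no contraception requirement, and section IV.C does not name pregnancy among the exit criteria, although its general safety grounds could cover it. The pre-dose test is thus the main named check behind criterion (5). No efficacy endpoint or analysis depends on this.

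**Working it through.** The plan states no figure to reproduce. The check compares the sections in order of time and then sets out the gap.

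**Step 1: which tests are called for, and when**

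| Point in time | Section | Pregnancy test called for? |
|---|---|---|
| Eligibility assessment after consent | V.A | None shown; list appears cut off |
| Any day in the four weeks before treatment | VI.A, item 13 | Yes, once |
| First dose, children | V.B | None stated |
| First dose, adults | V.C, item 1 | None stated |
| Weekly in month 1 | VI.B | None named; adverse-reaction review |
| Month 1 drug level | V.C, item 3 | None named; blood sample for drug concentration |
| Months 3 and 6 | VI.B | Yes, by reference to the pre-trial list |
| After treatment | VI.C | Yes, by reference to the pre-trial list |

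In the text supplied, exactly one test precedes the first dose. The next scheduled one is at month 3, on treatment. The contacts in month 1 could raise suspicion of a pregnancy, but they come after dosing has begun and none prescribes a test.

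**Step 2: size of the gap**

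Let g be the number of days from the screening test to the first dose. Section VI.A allows four weeks, so g runs from 0 to 4 × 7 = 28 days.

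**Step 3: what a first-dose test changes**

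No test detects a conception immediately. Let L be the days before a conception becomes detectable. The documents give no value for L, and none is needed here:

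- conceptions that can go undetected at the first dose, as written: those of the last g + L days;
- the same with a test on the day of the first dose: those of the last L days;
- difference: (g + L) − L = g, whatever L is.

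| Test-to-dose gap g | Days closed by a first-dose test | Days still open |
|---|---|---|
| 0 | 0 | L |
| 14 | 14 | L |
| 28 | 28 | L |

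These are calendar days, not numbers of pregnancies. The documents give neither the distribution of g, nor a conception rate, nor a count of women of childbearing age, so an expected number of exposed pregnancies cannot be derived.

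**Step 4: number of extra tests**

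Each woman of childbearing age needs at most one extra test, and none if her item 13 test is done on the day of the first dose. Section III, item 3, sets a minimum enrolment of 20. If exactly 20 patients enrolled, the extra tests could not exceed 20 × 1 = 20. Because 20 is a floor on enrolment, it does not cap the number of tests in the trial.

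**The case against.** The strongest objection is that the absence of a repeat test cannot be proved from this text. The list in section V.A breaks off after vital signs. It shows none of the liver and kidney checks that inclusion criterion (4) needs, so it is visibly incomplete, and the consent pages were removed. This stands, and it limits the point to the text supplied. It does not remove the point: sections V.B, V.C and VI.A are natural places for a first-dose test, show no sign of being cut off, and contain none.

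A second objection is that this is a preference about timing. The plan does exclude pregnancy, tests for it before treatment and repeats the test later, and the same window covers every other baseline item. It is true that there is no internal contradiction. But pregnancy status can change within the window, and the remedy is the test already listed, placed on a particular day.

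A third objection is that a site may already test on the day of the first dose, which the window permits. In that case nothing is gained and nothing is lost.

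Three stronger readings are tempting and should be resisted:

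- A reader might infer that pregnancy is never tested again. Sections VI.B and VI.C repeat the test by reference to the pre-trial list.
- A reader might infer that a first-dose test would shorten exposure up to month 3. It would not: a woman who conceives just after a negative first-dose test faces the same interval to the month-3 test.
- A reader might infer that a stated share of exposed pregnancies would be avoided. The documents supply nothing from which to calculate one.

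**Conclusion.** The point holds for the period before the first dose. As the supplied text reads, criterion (5) can be satisfied by a pregnancy test up to 28 days old, and neither dosing section asks for a current result. Closing the gap removes 0 to 28 days between test and first dose, depending on when the site tests.

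The conclusion rests on two conditions: that no repeat test is stated in the part of section V.A that appears cut off or in other text not supplied, and that at least some women are screened before the day of the first dose. The number of women concerned is unknown. This is a participant-safety improvement worth considering; it has no bearing on the efficacy results.

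**What to change.** In section VI.A, item 13, add one sentence: every female of childbearing age must have a negative urine or blood pregnancy test on the day of the first dose, with the result read before intake, and any test done earlier in the four-week window must be repeated that day. State that this applies to both dosing regimens, with a cross-reference in sections V.B and V.C. If the full section V.A already contains such a requirement, the cross-references are enough.

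The cost is the added protocol text and at most one extra urine test per woman of childbearing age enrolled. No endpoint or analysis changes. The amendment will not detect a very recent conception, and it leaves testing after the first dose as it is.

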### **B. Evaluation during sirolimus treatment**

Adverse reactions are evaluated weekly during the first month of drug treatment. The efficacy and safety are then evaluated at the 3rd and 6th months, and the content of the examination is the same as the pre-trial evaluation.

- 1) Efficacy assessment:
  - a. Clinical symptom assessment (including VAS pain score, gastrointestinal bleeding, quality of life (Qol) evaluation, frequency of blood transfusion treatment and other related symptoms);
  - b. Changes in hemoglobin;
  - c. Coagulation I+D-dimer examination;
  - d. Nutritional status (including albumin, etc.);
  - e. Ultrasound, MRI examination of the lesion, abdominal and pelvic cavity contrast-enhanced CT + small intestine reconstruction CT examination, digestive system endoscopy to measure the size, quantity and total load of VM lesions;
- 2) Safety assessment: Safety parameters (such as asking adverse events, measuring laboratory values, vital signs, gastrointestinal bleeding, etc.) will be closely monitored on a regular basis throughout the study.
- 3) Treatment compliance: In order to monitor compliance, subjects are required to complete an electronic diary during the entire study period. Dates of drug intake will be tracked by this diary. At every visit, the investigator and the subject will review the electronic diary data together.

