**VIII. Statistical analysis**

**IX. Measures of quality control**

**X. Expected research results**

**XI. Potential risks, benefits or advantages of this study**

**XII. Data preservation and confidentiality**

**XIII. Measures to protect subjects and minimize risks**

## I. Background

Blue rubber bleb nevus syndrome (BRBNS) is a rare systemic syndrome featuring venous malformation and hemangiomas. Affected organs include skin and gastrointestinal tract. Patients manifest venous malformation (VM) at birth. Main histologic features of VM are dilated and distorted veins surrounded by sparse and irregular smooth muscle cells. The size and number of VM lesions in BRBNS increase gradually with age. Patients' skin develops 1-2cm of blue-violet, compressible, and hyperkeratotic VM lesions, mostly in palms and soles. Lesions cause local deformity, pain and intravascular coagulopathy. The latest manifests elevated D-dimers and may lead to disseminated intravascular coagulation (DIC). Risk of DIC is even higher under surgical treatment. Lesions of BRBNS can be found in the mucosa of the whole gastrointestinal tract. Small intestine is the most commonly affected organ. Lesions can cause gastrointestinal bleeding, intussusception, intestinal torsion and even intestinal necrosis. Due to long-term chronic gastrointestinal bleeding, many patients need to take life-long iron supplementary treatment and receive blood transfusions repeatedly. VM lesions of BRBNS can also affect organs in pelvic, abdominal and thoracic cavity. BRBNS is such a devastating disease, traditional drugs such as glucocorticoids, interferon- $\alpha$ , propranolol and intravenous iron are not effective. Besides surgical resection of affected tissue and repeated sclerotherapy, there is no validated targeted drug treatment.

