### **III. Research Design**

1. This study is a prospective, nonrandomized, open-label, single-arm clinical trial. The sirolimus capsule (Rapamycin, Yixinke®), 0.5 mg/grain\*20/box, is produced by North China Pharmaceutical Co., Ltd.
2. All patients who meet inclusion criteria and sign informed consents receive sirolimus treatment for at least 6 months. Patients are followed up in a regular schedule.
3. No less than 20 patients should be enrolled.

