### **B. Contents of statistical analysis**

- 1) General data analysis: Demographic variables and baseline characteristics will be summarized comprehensively by mean of descriptive statistics and/or appropriate frequency tables.
- 2) Evaluation of efficacy: According to follow-up and reexamination results, the patients' quality of life, size and volume of the lesions, tumor load control and improvement of symptoms will be analyzed.
- 3) Analysis of adverse events: Side effects and adverse events during medication will be assessed.
- 4) Evaluation of the relationship between adverse events and the tested drug

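### VAS pain is read as change from baseline in a single arm, but analgesic use is neither held constant nor used in the analysis, so an analgesic change cannot be separated from a sirolimus effect

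*Combined protocol and SAP*

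**What the plan says.** - **Design.** Section III: "This study is a prospective, nonrandomized, open-label, single-arm clinical trial". On sample size: "No less than 20 patients should be enrolled".
- **Pain as an efficacy measure.** Section VI.B, item 1a: "Clinical symptom assessment (including VAS pain score, gastrointestinal bleeding, quality of life (Qol) evaluation". Coagulation is item 1c of the same list: "Coagulation I+D-dimer examination".
- **Timing.** Both are measured in the four weeks before treatment (VI.A). On treatment, "The efficacy and safety are then evaluated at the 3rd and 6th months". They are repeated at the end of therapy and six and twelve months afterwards (VI.C).
- **Disease background.** Section I: "Lesions cause local deformity, pain and intravascular coagulopathy". It also links the coagulopathy to raised D-dimers.
- **Other drugs.** Iron is the only concomitant drug with a rule. Under V.C it is "not considered as study treatment and will be recorded as concomitant medication". Analgesics and anticoagulants are not mentioned anywhere.
- **Analysis.** Section VIII.A is descriptive, with 95% confidence intervals. Section VIII.B(2) ends its list of efficacy outcomes with "tumor load control and improvement of symptoms will be analyzed". It does not refer to other treatment.

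**The concern.** With no control group, nothing cancels the effect of treatment given alongside sirolimus. The protocol itself says the disease is painful, so analgesic use during at least six months of treatment is foreseeable. A patient who starts an analgesic after the baseline score and has a lower VAS at month 3 contributes that whole fall to the sirolimus result. The reverse also matters: if sirolimus relieves pain and the patient gives up an analgesic, VAS may not change and a real benefit goes unseen.

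At stake is whether the pain result can be interpreted. Bias of this kind does not shrink as more patients are enrolled, and it is hard to undo later if starts, stops and dose changes were not recorded when they happened.

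**Working it through.** The plan gives no figure to reproduce: the minimum of 20 patients comes with no effect size, standard deviation, alpha or power. The check is therefore a reading of the documents followed by an illustration.

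**Step 1. Is analgesic use held constant?** Section IV.A (inclusion) and IV.B (exclusion) set no stable-dose, washout or prohibited-drug rule for analgesics. Exclusion 4 concerns diseases and conditions at entry. The exit criteria (IV.C) name surgery, compliance and safety, not a change in other drugs. The rejection criteria (IV.D) remove protocol violators, but there is no co-treatment rule to violate. Answer: no.

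**Step 2. Is it used in the analysis?** Section VIII has no adjustment, no stratification, no rule for a change in other treatment and no sensitivity analysis. Answer: no.

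**Step 3. How far could the mean VAS change move?** Inputs: n = 20 (section III minimum); k patients start an analgesic; each one's VAS falls by d points for that reason. The values of k and d are assumptions, and d = 3 presumes a 0 to 10 scale, which the protocol does not state.

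Shift in mean = k × d / n

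- k = 2: 2 × 3 / 20 = 0.3 points
- k = 4: 4 × 3 / 20 = 0.6 points
- k = 6: 6 × 3 / 20 = 0.9 points

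These are falls with no sirolimus effect at all. If instead k patients stop an analgesic that had been holding VAS d points lower, the same formula gives 0.3 to 0.9 points in the other direction. Because k / n is a share of patients (here 10% to 30%), the shift is the same in a larger trial with the same share, while the confidence interval becomes narrower.

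**Step 4. Could it look like an effect?** A simulation with n = 20 and zero sirolimus effect used a one-sample t interval at 95%, with 40,000 repeats per setting. Each patient starts an analgesic with probability f. Assumed ranges: d = 1 to 3 points, SD of change = 1.5 to 2.5.

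| Share starting, f | Expected mean fall, f × d | Chance the interval excludes zero on the benefit side |
|---|---|---|
| 10% | 0.1 to 0.3 | about 4% to 9% |
| 25% | 0.25 to 0.75 | about 6% to 34% |
| 40% | 0.4 to 1.2 | about 10% to 68% |

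The nominal figure is 2.5%. No calculation was made for D-dimer, because the documents give no D-dimer values.

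**The case against.** The strongest reply is that the premise comes from outside the documents. They never mention analgesics, and that analgesics lower VAS is general pharmacology. The figures above multiply assumed inputs; they show that bias is possible, not that it is likely. VAS is also one item in a long, unranked list that includes imaging, endoscopy and hemoglobin. All of this stands and limits the size of the claim. It does not remove the defect: in a single arm, the plan as written offers no way to tell the two sources of change apart.

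Recording is also partly covered. The rule for iron implies a concomitant-medication record. The baseline content, including medical history, is repeated at later visits. Treatment given for an adverse event goes into the case report form (section VII, Record and report), which would catch an analgesic for worsening pain. A reader should therefore not infer that analgesic use is never recorded. But these routes need not capture a dose change for stable lesion pain, or a stop, and the compliance diary in VI.B is described for tracking study drug intake. Even complete records would not be used under section VIII.

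Three other stronger readings are tempting and are not supported:

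- **A shift of 10 to 30 percentage points in patients improved** (2/20 to 6/20). The protocol defines no responder on VAS, so there is no such proportion to shift.
- **Equal weight for D-dimer.** It is an efficacy assessment in VI.B, but VIII.B(2) does not name it among the outcomes analysed. Nothing in the documents suggests that anticoagulants would commonly be started; section I describes chronic gastrointestinal bleeding.
- **Distortion of the month-3 adult dosing decision.** Section V.C refers to improvement without saying that VAS or D-dimer decides it.

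**Conclusion.** The concern holds for VAS pain. Following the plan as written can credit an analgesic effect to sirolimus, or hide a sirolimus benefit when analgesics are reduced. The size cannot be found from the documents. Under the assumptions that 2 to 6 of 20 patients start an analgesic and that each loses 3 VAS points because of it, the mean change is off by 0.3 to 0.9 points. Smaller shares or weaker effects give less.

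For D-dimer the same logic applies in principle, but its place in the analysis is undefined and no size can be given. It supports recording and a sensitivity listing, and no more.

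**What to change.** 1. **Sections VI.A to VI.C:** at each VAS assessment, record analgesic drug, dose and start and stop dates, extending the concomitant-medication record already implied for iron. Record anticoagulant use at the same visits.
2. **Section VIII.B(2), pain:** keep the all-patient summary of VAS change. Add one pre-stated analysis in which a VAS fall with a new or increased analgesic since baseline is not counted as pain improvement, and report analgesic reductions alongside. The size of VAS fall that counts must be stated in advance, because the protocol gives none.
3. **Section VIII.B(2), D-dimer:** summarise all patients, and flag those with an anticoagulant change since baseline in a sensitivity listing. Do not limit the main summary to patients without a change: that selects on a post-baseline event and shrinks a sample that may be only 20.

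The cost is a few extra entries at existing visits, one analysis rule and a possibly less favourable pain result. No restriction on care is proposed.
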